6.1 Inclusion Criteria

Subjects are eligible for inclusion in the study only if they meet all of the following criteria at screening as specified in the criteria below:

1. Are healthy male or female subjects, as determined by medical history and physical examination
 - a. Male subjects must adhere to contraception restrictions specified in Section 6.3.5:
 - b. Female subjects of non-childbearing potential due to:
 - i. Menopause: spontaneous amenorrhea for at least 12 months not induced by a medical condition such as anorexia nervosa and not taking medications that induced the amenorrhea (e.g., oral contraceptives, hormones, gonadotropin releasing hormone, anti-estrogens, selective estrogen receptor modulators, or chemotherapy)
 - ii. Surgical sterilization
2. Are aged at least 21 to 65 years, inclusive, at screening
3. Have a body mass index of 18 to 35 kg/m², inclusive, at screening
4. Have clinical laboratory test results within normal reference range for the population or investigative site, or results with acceptable deviations that are judged to be not clinically significant by the investigator at screening and enrollment
5. Have an estimated glomerular filtration rate ≥ 60 mL/minute/1.73 m² at screening and enrollment;
6. Have venous access sufficient to allow for blood sampling as per the protocol
7. Are reliable and willing to make themselves available for the duration of the study and are willing to follow study procedures

8. Are able and willing to give signed informed consent approved by the sponsor and the Institutional Review Board (IRB) governing the site

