## **7.5      Baseline Definition**

The baseline is the results measured at Visit 3 prior to dosing or Visit 2 if Visit 3 is not available.

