### 9.3 Laboratory Tests

The test results of clinical chemistry, hematology and urinalysis are to be summarized by visit. Change from baseline to each post-baseline visit will also be provided. When applicable, all the test result in the following list will be presented.

Clinical Chemistry:	Hematology:
Alkaline phosphatase	Erythrocytes count (RBC)
Alanine Aminotransferase	Hematocrit
Aspartate Transaminase	Hemoglobin
Albumin	Mean cell volume
Blood urea	Mean cell hemoglobin
Bicarbonate	Mean cell hemoglobin concentration
Total Bilirubin	Leukocyte count (WBC)
Calcium	Platelets
C-reactive Protein	Basophils
Complement 3	White blood cell count + differential
Complement 4	Erythrocyte sedimentation rate (ESR)
Sodium	
Total cholesterol	Urinalysis:
Chloride	pH
Creatinine	Specific gravity
Glucose	Blood
Potassium	Nitrite
	Bilirubin
	Ketones
	Protein
	Glucose
	Urobilinogen
	Leukocytes
	Microscopy

Additional analysis will be performed to C3, C4, CRP and ESR.

The number and percentage of subjects with significant decrease in C3 and C4 will be summarized at each of the scheduled visits by treatment and by cohort.

The number and percentage of subjects with significant increase in CRP and ESR will be summarized at each of the scheduled visits by treatment and by cohort.

The significant decrease in C3/C4 will be met if the lab result is classified as NORMAL at baseline, and classified as LOW (<LLN) at post-baseline visits, OR the lab result is classified as LOW at baseline(<LLN), and result gets LOWER than baseline at post-

baseline visits. The significant increase in CRP/ESR will be met if the lab result is classified as NORMAL at baseline, and classified as HIGH ( $>\text{ULN}$ ) at post-baseline visits, OR the lab result is classified as HIGH at baseline( $>\text{ULN}$ ), and result gets HIGHER than baseline at post-baseline visits.

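### SAP 9.3 has no route for a complement fall from HIGH to LOW, so Table 14.3.4.4 would report it as no significant decrease

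*SAP*

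**What the plan says.** SAP 9.3 (Laboratory Tests) adds a responder count for C3, C4, CRP and ESR to the ordinary by-visit summaries. For C3 and C4 a significant decrease is met in one of two ways. The first is that "the lab result is classified as NORMAL at baseline, and classified as LOW (<LLN) at post-baseline visits". The second is that "the lab result is classified as LOW at baseline(<LLN), and result gets LOWER than baseline" at a later visit. CRP and ESR have the mirror rule for increases: "The significant increase in CRP/ESR will be met if the lab result is classified as NORMAL at baseline, and classified as HIGH" afterwards, or HIGH at baseline "and result gets HIGHER than baseline at post-baseline visits". None of the four routes states a minimum size of change.

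Baseline is a single result (SAP 7.5): "The baseline is the results measured at Visit 3 prior to dosing or Visit 2 if Visit 3 is not available". The shell for Table 14.3.4.4 gives N, YES and NO at each post-baseline visit. Neither 9.3 nor the shell removes any baseline class from N.

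Out-of-range subjects can enrol. Protocol 6.1, criterion 4, accepts "results with acceptable deviations that are judged to be not clinically significant by the investigator at screening and enrollment", and Protocol 6.1 and 6.2 set no numerical limit for these four tests.

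**The concern.** The two C3/C4 routes cover baselines that are NORMAL or LOW. HIGH is left out. A subject who starts above the upper limit and ends below the lower limit has fallen further than any subject who reached the same end value from a normal baseline, yet is tabulated as NO.

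Protocol 9.4.5.2 names complement, CRP and ESR among the laboratory checks for vasculitis and other type 3 hypersensitivity. Protocol 3.3 gives vasculitis as the dose-limiting toxicity in monkeys and attributes it to immune complexes and complement activation. Table 14.3.4.4 is the only place where the SAP counts subjects with an adverse shift in these markers. The shift table in SAP 9.4 is for ECG assessments only.

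A second, lesser issue is that the already-abnormal route treats a further adverse change of any size as significant, so ordinary variation can be counted.

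**Working it through.** The plan states no figure for this rule, so there is none to reproduce. The first step is a check of the logic and needs no distributional assumption. The later steps size the effect and do need assumptions.

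**1. Logic of the C3/C4 rule.** The limits 0.9 and 1.8 are arbitrary and serve only as illustration.

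| Baseline → later | Class change | Fall | SAP 9.3 | With 'not LOW' at baseline |
|---|---|---|---|---|
| 1.85 → 0.70 | HIGH → LOW | 1.15 | NO | YES |
| 1.20 → 0.80 | NORMAL → LOW | 0.40 | YES | YES |
| 0.91 → 0.89 | NORMAL → LOW | 0.02 | YES | YES |
| 0.89 → 0.88 | LOW → lower | 0.01 | YES | YES |
| 0.89 → 0.92 | LOW → NORMAL | none | NO | NO |
| 1.85 → 1.50 | HIGH → NORMAL | 0.35 | NO | NO |

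The first row is the error. For CRP/ESR, HIGH → LOW is rightly not counted, because it is not an increase. The mirror gap there is LOW → HIGH. It can arise only if the laboratory reports a lower limit, which the documents do not say.

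**2. Inputs for size.**
- From the documents: 6 active and 2 placebo per cohort (SAP 4), and 7 cohorts with subjects (SAP 6). This gives 7 × 6 = 42 active and 7 × 2 = 14 placebo as planned.
- The number of post-baseline tests, K, is 4 as the SAP schedule reads and 5 as the protocol schedule reads. The tables may be damaged in extraction, so both are used.
- Assumed: reference limits at the 2.5th and 97.5th percentiles, normal values, within-subject correlation 0.5 to 0.9, and no drug effect.

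**3. How many start LOW.** 42 × 0.025 = 1.05 active subjects per analyte. The chance of at least one is 1 − 0.975^42 = 65%. For placebo, 14 × 0.025 = 0.35. These scale directly with the assumed 2.5%.

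**4. How often an unaffected LOW-baseline subject is flagged.** Simulation of 2,000,000 no-effect subjects gave the following. Ranges are K = 4 to K = 5.

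| Correlation | Flag per visit, given LOW baseline | Flag at least once, given LOW baseline | Subjects of 42 ever flagged: LOW → lower | Subjects of 42 ever flagged: NORMAL → LOW |
|---|---|---|---|---|
| 0.5 | 0.09 | 0.27–0.31 | 0.28–0.32 | 2.78–3.30 |
| 0.7 | 0.17 | 0.41–0.45 | 0.43–0.47 | 2.06–2.42 |
| 0.8 | 0.22 | 0.49–0.54 | 0.52–0.57 | 1.62–1.86 |
| 0.9 | 0.30 | 0.59–0.64 | 0.62–0.67 | 1.08–1.23 |

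Two closed forms use a stable true level and independent variation between visits:
- True level well beyond the limit: the baseline and K later values are exchangeable, so the baseline is the lowest with probability 1/(K+1). The chance of at least one flag is K/(K+1): 4/5 = 80% and 5/6 = 83%.
- True level exactly at the limit, with baseline beyond it by chance: 1 − 2[1 − 0.5^(K+1)]/(K+1). For K = 4 this is 1 − 1.9375/5 = 61%. For K = 5 it is 1 − 1.96875/6 = 67%.

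Across these models the range is 27% to 83%. Treating the baseline as measured without error would give 1 − 0.5^4 = 94% to 1 − 0.5^5 = 97%. That ignores regression toward the mean after an out-of-range baseline, so it is not used.

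**5. How often HIGH → LOW occurs without a drug effect.** The expected number among 42 active subjects was 0.0007 to 0.0010 at correlation 0.5, and no such case appeared in the simulation at 0.7 or above.

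**The case against.** The best defence is that little depends on this table. SAP 9.3 also requires results and change from baseline at each visit, and SAP 7.1 adds minimum and maximum, so an extreme complement fall would show there. Individual values should be available from Listing 8.4 or, under SAP 12.2, from raw-data listings judged to suffice. Protocol 9.2 requires investigators to document their review of each laboratory safety report. Clinical vasculitis or hypersensitivity would be counted in the adverse-event tables. Dose escalation and stopping (Protocol 7.4.1) do not use Table 14.3.4.4. All of this stands. It limits the consequence but does not make NO the right entry.

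The already-abnormal route also has a real defence. It follows the same emerging-or-worsening idea as the definition of a treatment-emergent event in SAP 9.1. Over-inclusion is cautious in a first-in-human safety summary, and pooled placebo is exposed to the same noise. The NORMAL-to-LOW route has no minimum size either and, under the assumptions above, yields more chance flags. This defence stands.

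A reader might infer that the rule misclassifies all four markers in both directions, or that most unaffected subjects would be flagged. The text does not support either. The HIGH-to-LOW gap concerns C3 and C4 only, and only further drift in the adverse direction is counted. The percentages for being flagged at least once apply only to subjects already out of range on the adverse side, and the by-visit shell does not report that quantity.

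**Conclusion.** The rule for C3 and C4 is incomplete as written: HIGH to LOW is reported as no significant decrease. This follows from the wording alone. The case should be very rare without a drug effect, so if it did occur it would more likely be real than noise. That makes the gap worth closing even though no data are lost and no planned decision depends on the table.

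For CRP and ESR the corresponding gap is LOW to HIGH, and it is conditional on the laboratory having a lower limit.

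The absence of a minimum change in the already-abnormal route is a matter of presentation, not an error. It would produce about 0.3 to 0.7 chance-flagged active subjects per analyte over the study under the simulated models, resting on the assumed 2.5% beyond the limit and correlation of 0.5 to 0.9. One such subject is 1/6 = 16.7% of a cohort's active group, so the reader of the table should be able to recognise it. It would be too strong to conclude that an immune-complex signal would be hidden from the study report, because the by-visit summaries remain.

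**What to change.** In SAP 9.3:
- For C3 and C4, replace the normal-at-baseline condition with not LOW at baseline (normal or high).
- For CRP and ESR, replace it with not HIGH at baseline. This changes nothing if the laboratory has no lower limit.

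In Table 14.3.4.4:
- Add a row for any post-baseline assessment, so that repeated flags in one subject can be told from single flags in several.
- Show subjects who became newly out of range separately from those who worsened from an out-of-range baseline, so that small drift can be recognised. This matters more once the any-visit row is added, because that row accumulates chance flags.

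The cost is a few words in the SAP, a few lines of programming and some extra table rows. No new data are needed, and the change to the baseline condition has no evident downside.

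A minimum-change threshold for the already-abnormal route is optional and not part of this request. It would lower sensitivity. The sponsor is not blinded (Protocol 5.4) and the SAP already refers to a data lock (SAP 6), so any threshold taken from trial data should be set without reference to post-dose results.

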## **9.4    Electrocardiogram**

Descriptive statistics of ECG parameters(quantitative) and assessments (qualitative) will be summarized at each visit. The change from baseline will be summarized as well for quantitative parameters at each visit. Shift tables from baseline will be presented for ECG qualitative assessment.

## **9.5    Neurological Examinations**

Descriptive statistics of Neurological Examinations will be summarized at each visit. The number and percentage of Neurological Examinations result will be presented as well.

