| PACAP sample ⁱ | | | Predose, EOI ^h 6, 12 h | 24 h | 48 h | | X | | X | | X | | X | | X | X |
| Immunogenicity sample | | | Predose | | | X | | X | | X | | X | | X | | X |
| Samples for infusion and hypersensitivity reactions ^j | | | Predose | | | | | | | | | | | | | |
| Non-genetic biomarker sample | | | Predose | | | X | | | | | | | | | | |
| PGx sample ^k | | | Predose | | | | | | | | | | | | | |

| Study Visit | 1 | 2 | 3 | 4 | 5 | 6 | 7 | 8 | 9 | 10 | 11 | 12 | 13 | 14 | 15 | 16 ^a |
|-------------------------|-----|----|---|---|---|---|---|--------------------|------------|------------|------------|------------|------------|------------|------------|---------------------|
| Study Day | -28 | -1 | 1 | 2 | 3 | 5 | 7 | 9 (-1 to +2) | 15 (±2) | 22 (±3) | 29 (±3) | 43 (±3) | 57 (±4) | 71 (±4) | 85 (±7) | 141 / ED (±7) |
| Visit Type | S | A | I | I | D | O | O | O | O | O | O | O | O | O | O | O |
| Adverse events | | | | | | | | | ← X → | | | | | | | |
| Concomitant medications | | | | | | | | | ← X → | | | | | | | |

Abbreviations: A = CRU admission; BP = blood pressure; CRU = clinical research unit; D = CRU discharge; ED = early discontinuation; EOI = end of infusion; h = hour; I = inpatient stay; m = minute; O = outpatient; C3 = total complement C3; C4 = total complement C4; CRP = C reactive Protein; ESR = erythrocyte sediment rate; PACAP = pituitary adenylate cyclase-activating polypeptide; PGx = pharmacogenomics; S = screening.

Note: if multiple procedures take place at the same time point, the following order of the procedure should be used: electrocardiogram, vital signs, and venipuncture. Unless otherwise specified, predose samples may be taken at any time prior to dosing, based on CRU activity schedule.

a in case of early discontinuation/withdrawal, the subject should undergo all Visit 16 activities.

b Height will be collected at Screening only.

c Full medical assessment prior to first dose (on Day -1 or Day 1), discharge, and discontinuation visits. Symptom-driven medical assessment as deemed necessary by the Investigator.

d Day -1 samples/activities could be collected/Performed up to 5 days before the scheduled day of dosing. The medical assessment, neurological examination and eligibility review may be performed pre-dose on Day 1. If screening visit is within 1 week (inclusive) of Day -1, neurological examination, ECG, hematology and chemistry do not need to be repeated.

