5.4 Scientific Rationale for Study Design

This study is designed to evaluate safety, tolerability, and PK of LY3451838 after single IV and SC dose administration in healthy subjects to provide the most unbiased assessment of safety and tolerability in this first-in-human study.

Hypersensitivity reactions, including both acute hypersensitivity reactions and immune complex diseases, are potential risks for all therapeutic antibodies, including LY3451838. Subjects with a history of clinically significant hypersensitivity reactions / conditions, or autoimmune diseases are excluded from the study to minimize risks for hypersensitivity reactions in the subjects in this study, and to avoid confounded interpretation of the safety data. Additional measures will be implemented to monitor and manage infusion reactions (Section 7.4.3.2), immunogenicity, and hypersensitivity reactions (Section 9.6.1). While vasculitis observed in the monkey toxicology studies was attributed to immune complex deposition, additional precautions, such as reviewing PK data before each dose escalation, limiting the dose range and implementing the exposure to that of the monkey NOAEL are designed into the protocol to address the uncertainty of the mechanism for vasculitis.

Because of the distribution of PACAP in the nervous system, and to follow-up on the subtle non-adverse changes in the neurological examination in the 2-month monkey toxicology study, neurological examinations will be performed to detect any early signals on the effects of LY3451838 on the nervous system.

Pharmacokinetic data will be used to guide dose escalation for all cohorts in Part A of the study; dose modification criteria are described in Section 7.4.1. Because the exposure after SC dosing is

[figure not shown]
expected to be less than with IV dosing for the same dose, sentinel dosing is not required in Part B of the study.

The predicted half-life of LY3451838 is 12 days, based on the allometric scaling from monkey PK data. A parallel-group design is used in both Part A and Part B of the study to avoid a prolonged washout period between doses and to avoid the potential to confound treatment-emergent antidrug antibody (TEADA) assessment. The monitoring period for this study is approximately 20 weeks after the last dose. This monitoring period duration supports adequate immunogenicity monitoring during the washout of LY3451838.

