## 9.2 Vital Signs

Vital signs (systolic and diastolic blood pressure, pulse rate and body temperature) are to be summarized at each visit. Change from baseline to each post-baseline visit will also be provided. When triplicate blood pressure or pulse rate measurement precede the orthostatic measurement, the last supine blood pressure or pulse rate measurement will be used.

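### The neurological summary table makes no comparison with baseline, so it does not separate new from pre-existing abnormalities or count subjects with any new one

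*SAP*

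**What the plan says.** SAP 9.5 has two sentences on the neurological examination: "Descriptive statistics of Neurological Examinations will be summarized at each visit" and "The number and percentage of Neurological Examinations result will be presented as well". The table list in SAP 12.1 gives it one table, 14.3.5.4. SAP 13 has no shell for that table.

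The neighbouring safety sections go further:

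- Vital signs (SAP 9.2): "Change from baseline to each post-baseline visit will also be provided".
- Laboratory tests (SAP 9.3): change from baseline as well, with C3, C4, CRP and ESR also classified against each subject's baseline value.
- ECG (SAP 9.4): change from baseline for the intervals, and "Shift tables from baseline will be presented for ECG qualitative assessment" (Table 14.3.5.3).

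Protocol 5.4 gives two reasons for the examination: where PACAP is found in the nervous system, and the monkey study. In its words, "to follow-up on the subtle non-adverse changes in the neurological examination in the 2-month monkey toxicology study, neurological examinations will be performed". The aim is early detection of effects on the nervous system.

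On baseline, SAP 7.5 says: "The baseline is the results measured at Visit 3 prior to dosing or Visit 2 if Visit 3 is not available". Footnote d to the schedule (Protocol Section 2, repeated in SAP 4.2) says: "If screening visit is within 1 week (inclusive) of Day -1, neurological examination, ECG, hematology and chemistry do not need to be repeated". The same footnote allows the neurological examination to be done before dosing on Day 1.

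**The concern.** A table of results by visit is a series of snapshots. It shows how many subjects were abnormal on a given day, but not whether they are the same subjects who were abnormal before dosing, nor how many different subjects were ever newly abnormal. The second count matters here because Protocol 3.2 describes the monkey effects as transient. A transient effect may appear in different subjects at different visits and leave each visit's percentage low.

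Protocol 9.4.1 already treats the subject's own baseline as the reference: abnormal examinations are to be repeated until the subject is back at baseline. The planned summary drops that reference. At stake is whether the report can state, by dose and against pooled placebo, how many subjects developed a new neurological finding, without a reader having to rebuild the number from listings.

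**Working it through.** The documents give no figure for this point, so there is nothing to reproduce. The check is what by-visit counts can and cannot determine.

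**Inputs**

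- 6 active and 2 placebo subjects per cohort (Protocol 5.1, SAP 4).
- Seven cohorts with data, since SAP 6 reports none enrolled in cohort 8. If filled as planned with no replacements: 7 × 6 = 42 active and 7 × 2 = 14 placebo.
- Four scheduled post-dose examinations in the SAP 4.2 schedule: Visits 4, 6, 10 and 16. The Protocol Section 2 schedule, as extracted, also seems to show Visit 12; a fifth visit would only widen the second range below.

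**Step 1: one post-dose visit against baseline.** Let *a* of *N* subjects be abnormal at baseline and *b* of *N* at a later visit, with complete data. The number newly abnormal lies between max(0, *b* − *a*) and min(*b*, *N* − *a*).

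| *N* | *a* | *b* | Lower | Upper |
|---|---|---|---|---|
| 6 | 0 | 1 | max(0, 1) = 1 | min(1, 6) = 1 |
| 6 | 1 | 1 | max(0, 0) = 0 | min(1, 5) = 1 |
| 6 | 1 | 2 | max(0, 1) = 1 | min(2, 5) = 2 |
| 6 | 2 | 2 | max(0, 0) = 0 | min(2, 4) = 2 |

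If nobody is abnormal at baseline, the count is exact. Once anyone is, it is not. For *a* = *b* = 1 the rate among those normal at baseline is either 0/5 = 0% or 1/5 = 20%, while the table shows an unchanged 16.7%. The bounds for these values of *a* and *b* are the same at *N* = 14 and *N* = 42.

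**Step 2: several post-dose visits, nobody abnormal at baseline.** If the visit counts are *b*₁ to *b*ₖ, the number of different subjects ever abnormal lies between the largest *b* and the smaller of *N* and the sum of the *b*'s. With 1 of 6 at each of four visits the range is 1 to 4 subjects: 1/6 = 16.7% to 4/6 = 66.7%. So a clean baseline removes the ambiguity at a single visit but not across visits.

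**Step 3: is a baseline always defined?** SAP 7.5 accepts Visit 3 predose, then Visit 2. Footnote d lets a site omit the Visit 2 neurological examination, ECG, hematology and chemistry after a recent screening. ECG, hematology and chemistry each have a scheduled Day 1 predose assessment to fall back on; the neurological row has none at Visit 3. A subject therefore has no baseline under SAP 7.5 only if all three hold: screening was within a week of Day −1, the examination was not repeated at Visit 2, and it was not done before dosing on Day 1. The documents do not say how many subjects this is.

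**The case against.** The strongest reply is that the information is not lost. Listing 12 shows neurological examinations by subject and visit, and SAP 12.2 drops the numbered listings only where raw-data listings suffice. With about six active subjects per cohort, comparing each with his or her own baseline by eye is feasible. The examiner is expected to know the baseline findings (Protocol 9.4.1), and a change recorded as an adverse event enters the treatment-emergent tables by cohort and against placebo. The subjects are healthy and exclusion 12 covers neurological disease, so baseline abnormalities should be uncommon. The examination is not a named endpoint, and the study is descriptive.

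Most of this stands, and it rules out the strongest reading: that the trial could not tell new abnormalities from old, or could not answer the question in Protocol 5.4. Two parts are weaker. A listing gives no rate by dose or against pooled placebo. And adverse event capture is uncertain for subtle findings: Protocol 9.4.1 says only that work-up of clinically significant changes should be considered, whereas Protocol 9.4.4.1 explicitly asks for clinically significant ECG diagnoses to be reported as events. A clean baseline also leaves Step 2 untouched.

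Two further inferences should be resisted. The neurological examination is not the only assessment tied to a monkey finding: C3, C4, CRP and ESR help follow the vasculitis finding (Protocol 9.4.5.2), and SAP 9.3 does compare them with baseline. Nor does every omitted Visit 2 examination leave a subject without a baseline, because a Day 1 predose examination satisfies SAP 7.5.

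**Conclusion.** The point holds for the summary table. SAP 9.5 and Table 14.3.5.4 do not separate new from pre-existing neurological abnormalities and do not count subjects with any new abnormality across visits. Only the subject listings would show this, together with adverse event reports where a change was recorded as one. The other main safety measures are compared with baseline, so the omission is out of line with the rest of the SAP.

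In a cohort of six, the uncertainty is 0 to 2 new cases when two subjects are abnormal at both times, and 1 to 4 subjects when one is abnormal at each of four visits. These are illustrations with assumed counts and complete data; the documents give no rate of baseline abnormality. The baseline gap is narrow and does not affect the table as now planned, which uses no baseline. It matters once a shift table is added. Overall this is a low-cost improvement to reporting, not a defect that prevents the trial from meeting its objectives.

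**What to change.** In SAP 9.5 and Table 14.3.5.4 add, by cohort, total LY3451838 and pooled placebo:

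1. A shift from baseline to the worst post-dose result, overall normal/abnormal, and by examination element if results are recorded that way. State whether unscheduled repeat examinations under Protocol 9.4.1 count towards the worst result.
2. The number and percentage of subjects with any new or worsened abnormality after dosing. Worsening can be counted only if the record grades or describes findings.

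In SAP 7.5 define the neurological baseline as the last examination before dosing, including the screening examination when footnote d was used and neither a Visit 2 nor a Day 1 predose examination was done.

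The cost is a few lines of SAP text and one short table, from examinations already performed. No visit or procedure changes. The overall shift follows the form already planned for the ECG interpretation. The documents do not show whether the case report form records results by element, so that part should be conditional.
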